7.11.1.2 Rate of Intubation, and any other Respiratory Support

Another key primary endpoint will be the rate of intubation by Day 14. That is, any occurrence of intubation (mechanical ventilation, or ECMO) at any point time in time between Days 1 and

14, will be considered to be an event. In addition, any intubation at any point during the study will be tabulated. The treatment arms will be compared using a Fisher's Exact or Chi2 test.

Furthermore, the various types of respiratory support will be summarized as specified below, including invasive ventilation (ventilator or ECMO), non-invasive ventilation by CPAP or BiPAP, high flow oxygen, low flow oxygen or no oxygen support required.

The durations of respiratory support (days) are defined as:

Duration of respiratory support

$$= \sum_{k_i=0}^{N_i} (\text{End Date/time on Day } k_i - \text{ Start Date/time on Day} k_i)/24$$

Where, N_i is the total number of available study days for any patient *i*. Respiratory support includes invasive ventilation, non-invasive ventilation and supplemental oxygen. Duration of oxygen support will be summarized by treatment arm; p-values generated from t-tests will compare the differences in the mean values between two treatment arms. These analyses will be generated for any oxygenation support, and for invasive ventilation separately.

Status of requiring respiratory support of each patient, including durations of any respiratory support (by type) will be listed.

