7.1 General Considerations

All safety analyses will be based on Safety Population; all efficacy analyses will be based on Modified Intent-to-Treat population, unless otherwise specified. Some specific sensitivity analyses of efficacy may be based on ITT and Per Protocol populations (for primary endpoints only). See Section 7.4 below for definitions of each analysis population.

All analyses will be considered as descriptive analyses. Derivation of two-sided 95% confidence intervals and p-values will be generated where applicable.

Time to event endpoints will be defined as the start date/time to the end date/time; censoring dates will be the last date/time the patient was determined to be event-free. Kaplan Meier methods will be used for time to event endpoint analyses; a log-rank test will be performed to compare the two survival curves. Timepoints estimates and median survival will be derived from the Kaplan Meier analysis. A Cox proportional hazards model may also be used to compare the two treatment arms using a hazard ratio.

Categorical endpoints will be calculated as the percentage of patients with the event, relative to the number of patients in a given analysis population (see Section 7.4). Stratified logistic regression approaches and/or repeated measures statistical approaches may be used to compare patients on the sargramostim and control arms, in addition to Fisher's Exact or Chi² tests (as appropriate). The randomization stratification factor for the baseline SOFA score (<6 versus \geq 6) will be considered for any stratified analysis.

Continuous endpoints will be summarized by n, means, medians, minimum, maximum, and 25th and 75th percentiles. Analysis of variance, analysis of covariance, and/or repeated measures statistical approaches may be used to compare patients on the sargramostim and control arms.

In the event that the underlying assumptions and/or distributions for a given statistical method are not satisfied, alternative statistical methods will be employed.

Additional exploratory analyses may be performed to evaluate the robustness and sensitivity of the study results, including but not limited to, additional evaluation of endpoints on other

analysis populations, subgroup analyses, treatment interactions, adjusted or stratified analyses, and/or alternative statistical methods.

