7.11.2.2 Mortality

Survival status will be collected up to Day 90 +/- 30 days. Death is considered as an event. All the mortality events and cause of death will be listed by treatment arm and by patient.

Patients who did not experience death within the first 90 days will be censored on the date of Day 90 visit or the date of last contact from the study which ever is earlier.

The number of patients who died and survival time will be summarized by treatment arm. Survival time will also be listed by patient. The probability function of death will be estimated by Kaplan-Meier method. The median time and its 95% confidence interval for each group will be reported. Cumulative progression rates estimated by the KM method for up to day 6, 14, 28, 90 and the 95% confidence intervals will be reported.

The hazard ratio will be estimated by the Cox proportional hazards model with treatment arm as a covariate in the model. Relevant hazard rates, hazard ratio between treatment arms and associated p-values will be tabulated.

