7.11.2.5 Hospitalization

The duration of hospitalization (days) is defined as:

Duration of hospitalization (Days) = Date of Discharge – Date of Randomization + 1. In this context, the date of hospital discharge is the earliest hospitalization discharge date on/after the treatment completion/discontinuation date from the Treatment Disposition CRF page. Moving a patient from ICU to a regular hospital ward, would not be considered as a hospital discharge date, in this case.

However, duration of ICU (days) = Date of ICU Discharge – Date of ICU admission + 1. In this context, moving a patient from ICU to a regular hospital ward, would be considered as ICU discharge date.

For patients who died in hospital prior to Day 28, alternative methods to account for these cases, such as assigning the duration of hospitalization as 28 days, may be considered.

Duration of hospitalization will be listed for each patient, and summarized by treatment arm.

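### The Day 14 intubation rate and the respiratory-support duration score an early death like a recovery, and the hospital-stay rule for deaths is left open

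*SAP*

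**What the plan says.** **Intubation by Day 14 (section 7.11.1.2).** This is half of the primary endpoint in section 5.2.1. The event is "any occurrence of intubation (mechanical ventilation, or ECMO) at any point time in time between Days 1 and" 14, compared between arms by Fisher's exact or chi-square test. Section 7.1 sets the denominator: "Categorical endpoints will be calculated as the percentage of patients with the event, relative to the number of patients in a given analysis population". Section 7.1.5 rules out imputation for the intubation rate.

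**Duration of respiratory support (section 7.11.1.2).** Start-to-end times are summed over study days, where the upper limit of the sum "is the total number of available study days for any patient". For the comparison, "p-values generated from t-tests will compare the differences in the mean values between two treatment arms". Death is not mentioned.

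**Hospital stay (section 7.11.2.5).** The stay runs from randomization to discharge, where "the date of hospital discharge is the earliest hospitalization discharge date on/after the treatment completion/discontinuation date". For in-hospital deaths before Day 28, alternative methods "such as assigning the duration of hospitalization as 28 days, may be considered".

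**Mortality (section 7.11.2.2).** Death is analysed on its own as a secondary endpoint, by Kaplan-Meier and Cox methods: "Cumulative progression rates estimated by the KM method for up to day 6, 14, 28, 90" are to be reported. The sensitivity analyses in section 7.11.1.3 repeat the primary analyses in the ITT and PP populations only.

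**The concern.** Death prevents later intubation and ends respiratory support. If a measure gives death no value of its own, an un-intubated death scores as a good result: no intubation, and a short time on support. The comparison between arms then depends partly on how many patients in each arm died before they could be intubated or weaned.

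This can work either way. More un-intubated deaths on sargramostim would flatter the drug. More on standard of care would hide a benefit. With equal rates, the difference in intubation rates is unaffected.

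Hospital stay is a different case. It ends at discharge, so for a patient who dies in hospital the value is not clearly defined. The plan recognises this but leaves the remedy optional. In an open-label trial, that choice could be made with the results by arm in view.

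**Working it through.** The SAP states no event rate, effect size or power, so there is no planned figure to reproduce. The inputs from the plan are the arm sizes (80 and 40, sections 6.1 and 7.2) and the rules above. All rates below are assumptions.

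**1. What one death does to the intubation rate.** An un-intubated death by Day 14 adds 0 to the numerator and 1 to the denominator, exactly as a recovery does. Compared with a definition that counts the death, each one lowers the arm's rate by 1/80 = 1.25 points on sargramostim or 1/40 = 2.5 points on control.

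**2. One set of counts.** Suppose 12/80 v 12/40 are intubated: 15% v 30%, Fisher p = 0.088. If 8 more sargramostim patients died un-intubated and no controls did, intubation or death is 20/80 v 12/40: 25% v 30%, p = 0.66. In the other direction, 16/80 v 8/40 intubated is 20% v 20%, p = 1.00. With 4 un-intubated control deaths, the composite is 16/80 v 12/40: 20% v 30%, p = 0.26.

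**3. How often the test favours sargramostim.** Intubation rate = composite rate − un-intubated death rate. All 81 × 41 possible tables were enumerated, counting two-sided Fisher p<0.05 with the lower rate on sargramostim. Each pair is sargramostim v control.

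| Intubated or dead | Un-intubated deaths | Intubation | Intubation test favours sargramostim | Composite test favours sargramostim |
|---|---|---|---|---|
| 25% v 25% | 5% v 5% | 20% v 20% | 2.1% | 2.1% |
| 25% v 25% | 7.5% v 5% | 17.5% v 20% | 4.4% | 2.1% |
| 25% v 25% | 10% v 5% | 15% v 20% | 8.7% | 2.1% |
| 25% v 25% | 15% v 5% (extreme) | 10% v 20% | 28.8% | 2.1% |
| 30% v 25% | 15% v 5% | 15% v 20% | 8.7% | 0.4% |

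In the third and fifth rows the observed intubation rate is lower on sargramostim in 72% of trials. In the fifth row the composite is truly worse on sargramostim.

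**4. Duration of support.** Assume one continuous episode from Day 1, a recovery hazard of 0.08 per day in both arms, and 28 days of follow-up. With h = recovery hazard + death hazard:

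- mean duration = (1 − exp(−28h))/h
- proportion dying on support = (death hazard/h) × (1 − exp(−28h))

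| Death hazard per day | h | Die on support | Mean days on support |
|---|---|---|---|
| 0.01 | 0.09 | 10.2% | 10.22 |
| 0.02 | 0.10 | 18.8% | 9.39 |
| 0.03 | 0.11 | 26.0% | 8.67 |

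For 0.03 (n = 80) v 0.01 (n = 40), the gap is 10.22 − 8.67, about 1.5 days. The SDs are 7.7 and 8.5, so the standard error is √(7.7²/80 + 8.5²/40) = 1.6 days, and the spurious gap is about one standard error.

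In simulated 80:40 trials, a pooled t-test favours the arm with more deaths at p<0.05 in about 17 to 18% of trials. At 0.02 v 0.01 the figure is about 8%, and with equal deaths about 2.5%. Welch's test gives about 14% and 6% for the two unequal cases.

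If support-free days to Day 28 are used instead, with death scored 0, the means for 0.03 v 0.01 are 14.1 v 15.8, in the correct direction. A Mann-Whitney test then favours the arm with more deaths in 0.2 to 0.3% of trials.

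**The case against.** **The endpoint is legitimate and deaths are reported.** The cumulative incidence of intubation, read beside mortality, is an interpretable quantity, and section 7.11.1.2 implements section 5.2.1 faithfully. The mortality analysis includes Day 14, and respiratory-support status and deaths are listed by patient. With about 120 patients, a reader could count the un-intubated deaths from the listings. This stands, and it is why the listed endpoint should stay. However, listings do not change the rate or its p-value, and two separate summary tables do not show how the two outcomes overlap.

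**The analyses are descriptive.** Section 7.1 says "All analyses will be considered as descriptive analyses" and section 7.2 states no hypothesis. This also stands: no formal error rate is lost. But p-values are planned for both measures, and a description that scores death as recovery can still mislead.

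**Other provisions might cover it.** Section 7.1 permits extra exploratory analyses and alternative methods, but they are optional and do not mention death. The ordinal scale may include death; its categories are in the protocol, which is not at hand. Section 7.11.1 qualifies its timepoints by data availability. Reading that as dropping un-intubated deaths from the denominator would conflict with section 7.1 and still not count the death as a bad outcome.

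**The sizes need strong assumptions.** The bias in the intubation difference is nil with equal un-intubated death rates, and the mild case only moves 2.1% to 4.4%. The duration cases need two or three times the death hazard with unchanged recovery. Mortality would then be observed to be higher in that arm in about 88% and 98% of trials. Part of the t-test figure comes from pooling unequal variances, and the SAP does not say which t-test is meant. These points limit the size, not the direction.

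**Support-free days have their own blind spot.** Death and survival on support through Day 28 both score 0. This is true, so deaths should be tabulated alongside.

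**Hospital stay.** Whether the value is missing or merely short depends on whether the CRF records death as an end of stay. The measure is only listed and summarised, with no test, so this is the smallest part of the point.

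**Conclusion.** The point holds and should be fixed. It follows directly from the SAP's event definition, denominator, no-imputation rule and duration formula that an un-intubated early death is scored like a recovery. Under moderate assumed imbalance (un-intubated deaths 10% v 5%), the chance of a nominally significant intubation result favouring the arm with more such deaths rises from 2.1% to 8.7%. For duration, a two- to three-fold death hazard gives a chance of about 8% to 18% with a pooled t-test.

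The size and direction in the actual trial depend on un-intubated deaths per arm, which the SAP does not give. The harm is a misleading estimate or p-value in a descriptive Phase 2 study that also reports mortality. That makes it worth correcting but not critical.

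**What to change.** Before the SAP is finalised:

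- **Section 7.11.1.2, intubation.** Keep intubation by Day 14 as the listed endpoint. Beside it, prespecify intubation or death from any cause by Day 14, in the same population with the same test. Tabulate by arm three exclusive outcomes: intubated, died un-intubated, alive un-intubated.
- **Section 7.11.1.2, duration.** In place of or alongside the t-test on raw durations, report support-free days and invasive-ventilation-free days through Day 28, with death scored 0 and a rank-based comparison. State how support after discharge is counted, and show the number of deaths next to the result.
- **Section 7.11.2.5.** Replace the optional wording with one fixed analysis rule for in-hospital deaths before Day 28.

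The cost is SAP text, one composite table and a few derivations. Survival status is already collected to about Day 90 (section 7.11.2.2), and support start and end times are already used in the duration formula. The downside is one more result to interpret beside the primary intubation rate.

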6.2 Randomization

Per Section 5.2 of the Study Protocol, randomization will be performed, using a 2:1 randomization ratio, with the strata defined as:

- investigational site,
- SOFA score (<6 versus ≥ 6)

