7.2 Sample Size

Approximately 120 patients will be randomized: of which 80 will receive sargramostim + SOC, and 40 patients who will receive SOC alone to evaluate the clinical efficacy and safety of sargramostim in patients with COVID-19 associated acute hypoxemia.

The sample size was based on practical and clinical considerations to ensure that the efficacy endpoints and safety profile could be appropriately evaluated and was not based on any statistical assumptions or hypotheses. As a result, the analyses of this study will be considered as descriptive analyses.

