7.7 Demographics and Baseline Disease Characteristics

Demographic information for MITT Population will be summarized. The demographic data consists of age, gender, race, ethnicity, baseline height, body weight, body mass index (BMI), Body Surface Area (BSA). The baseline disease assessment scales, including the SOFA score (including categorization of <6 versus \geq 6), ordinal scale, and National Early Warning System 2 Score will be summarized. The baseline COVID-19 diagnostic information will also be summarized.

Individual demographics and other baseline factors will be listed by patient.

Continuous variables (for example, age, height, body weight, body mass index, body surface area, disease assessment scales) will be summarized by n, means, medians, minimum, maximum, and 25^{th} and 75^{th} percentiles. Number of patients and percentages will be used to describe categorical (discrete) variables (for example, gender, race, ethnicity and SOFA score <6 versus ≥ 6).

If there is a difference between the MITT and the Safety Population, the summary of baseline and disease characteristics may be repeated on the Safety Population.

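### Day 14 intubation, a primary endpoint, gets only a crude two-by-two test; a prespecified covariate-standardized risk difference would recover a modest amount of precision and settle whether to adjust

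*SAP*

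**What the plan says.** - **Intubation (SAP 7.11.1.2).** Any intubation in Days 1 to 14 counts as an event. The whole comparison is: "The treatment arms will be compared using a Fisher's Exact or Chi2 test". No effect estimate or covariate is named.
- **Mortality (SAP 7.11.2.2 and 7.1).** "The hazard ratio will be estimated by the Cox proportional hazards model with treatment arm as a covariate in the model". Section 7.1 adds that "a log-rank test will be performed to compare the two survival curves", without mentioning strata.
- **Baseline data.** Section 7.11.1.1 derives the gradient from arterial blood gas, and 7.11.1 says the blood gas was required at baseline. Section 7.7 states "The demographic data consists of age, gender, race, ethnicity" among the items collected.
- **The other primary endpoint (SAP 7.11.1.1).** The repeated-measures model for the gradient includes its baseline value as a continuous covariate. The responder analysis in the same section lists a stratified logistic model as an alternative; the intubation text does not.
- **General rules (SAP 7.1).** Logistic regression for categorical endpoints is permitted in addition to the simple tests, with baseline SOFA (<6 versus ≥6) as the only factor named. Adjusted analyses appear again as an exploratory possibility, with no covariates listed.
- **Design.** The trial is open-label (6.1). Section 6.2 says "randomization will be performed, using a 2:1 randomization ratio, with the strata defined as" site and SOFA. Section 7.2 gives about 120 patients, "of which 80 will receive sargramostim + SOC, and 40 patients who will receive SOC alone", and says the size "was not based on any statistical assumptions or hypotheses".

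**The concern.** The plan adjusts one primary endpoint for baseline and leaves the other crude, although baseline gas exchange and age are natural candidates to predict intubation. With 40 controls, a chance difference in severity at entry passes straight into the crude risk difference.

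Two things are at stake. The first is precision. The trial has no power basis and calls its analyses descriptive, so the estimate and its interval are its main product. The second is prespecification. Because adjustment is allowed but not defined, it could be chosen, and its covariates picked, after the imbalance and the result have been seen. The open-label design makes that a practical worry.

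**Working it through.** **Inputs.** From the SAP: 80 and 40 patients, the crude test, and the planned baseline variables. The SAP gives no event rate, effect size or prognostic strength, so there is no figure of its own to reproduce. Those inputs are assumptions below, shown over a range.

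**1. Chance imbalance.**
- Factor present in 50% of patients: SD of the between-arm difference = √[0.25 × (1/80 + 1/40)] = √0.009375 = 0.0968. A 10-point difference is z = 0.10/0.0968 = 1.03, so the two-sided probability is 0.30.
- Continuous covariate in SD units: SD = √(1/80 + 1/40) = 0.194. A difference above 0.25 SD has probability 19.7% for one covariate and 1 − (1 − 0.197)² = 35.5% for at least one of two independent covariates.

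**2. Effect on the estimate.** If risk is 30% with the factor and 10% without (assumed), a 10-point imbalance moves the risk difference by 0.10 × 0.20 = 2 points. At a 20% event rate the crude SE is √[0.20 × 0.80 × (1/80 + 1/40)] = 7.7 points, so the shift is about a quarter of one SE.

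**3. Precision gain.** Simulation of 80:40 trials, 3,000 per setting, intubation 30% (control) versus 15%, with two independent continuous covariates standing for the gradient and age. The adjusted estimate is the risk difference standardized from a logistic model; the adjusted test is its likelihood-ratio test.

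| Odds ratios per SD | SD crude | SD adjusted | Variance ratio | 95% half-width (1.96 × SD), points | Rejection: Fisher / chi-square / adjusted |
|---|---|---|---|---|---|
| 1.0, 1.0 | 0.0841 | 0.0848 | 1.016 | 16.5 → 16.6 | 43.8 / 48.6 / 47.1% |
| 1.5, 1.3 | 0.0832 | 0.0817 | 0.963 | 16.3 → 16.0 | 45.8 / 50.6 / 51.2% |
| 2.0, 1.5 | 0.0827 | 0.0799 | 0.932 | 16.2 → 15.7 | 45.5 / 49.9 / 52.6% |
| 2.5, 2.0 | 0.0837 | 0.0758 | 0.821 | 16.4 → 14.9 | 43.8 / 48.5 / 53.8% |

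- With odds ratios 2.0 and 1.5, the variance ratio is 0.949 at 20% versus 10% and 0.906 at 40% versus 20%.
- A further simulation under assumed settings gave a reduction between roughly none and 16%, and a loss of about 3% when the covariates were not prognostic.
- With equal 30% rates, the adjusted test rejects in 4.8 to 5.5% of trials, so error control is not harmed.

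**4. Imbalance and precision are one effect.** Across the prognostic 30% settings (equal rates and 30% versus 15%), the crude estimate correlates 0.22 to 0.43 with the imbalance; after adjustment the correlation is about 0. Squared, 0.22² = 0.05 and 0.43² = 0.18, close to the 4% and 18% variance reductions. The two consequences should not be counted twice.

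**5. Mortality.** Simulation with 80:40 allocation, 90-day follow-up, assumed hazard ratio 0.6, about 18 to 20% deaths, 400 trials per setting. After adding a covariate with log hazard ratio 0.7 or 1.0 per SD, the mean SE of the treatment log hazard ratio rose from 0.453 to 0.458 and from 0.420 to 0.427. A repeat gave 0.451 to 0.456 and 0.424 to 0.432. At 1.0 per SD the mean estimate moved from −0.44 to −0.52.

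**6. Events available.** At 30% versus 15%: 40 × 0.30 + 80 × 0.15 = 24 events. At 20% versus 10%: 8 + 8 = 16. A model with arm and three covariates then has 24/4 = 6 or 16/4 = 4 events per term.

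**The case against.** **A crude test is valid in a randomized trial, and the SAP contradicts nothing by using one.** This stands. Chance imbalance is part of the sampling variation that the crude test and interval already allow for. A reader might infer that the intubation result would be biased; the design does not support that.

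**Adjustment is not excluded.** This also stands. Section 7.1 permits it, so it would be wrong to say that the plan forbids it. But permission without a model or covariate list is not prespecification.

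**SOFA stratification already controls severity.** Partly. Section 7.11.3.2 lists the respiratory system among six SOFA components, so the stratum carries some information on hypoxemia. The documents do not show how much. They support adding the gradient to the stratum, not dismissing the stratum.

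**The gain is small and rests on assumptions.** Largely true. A variance reduction of 27% can be obtained, but it needs a log-odds of 1.4 per SD, an odds ratio of about 4, which nothing in the SAP supports. Power rises by only 0.6 to 5.3 points over chi-square in the prognostic settings. The larger gap to Fisher's test (5.4 to 10.0 points) partly reflects how conservative that test is.

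**Adjustment could lose patients.** Fair. Baseline blood gas is required, but section 7.11.1 also qualifies the primary analyses by data availability, and 7.1.5 rules out imputing the gradient. It is not established that every patient has a baseline value. The intubation analysis currently needs no blood gas; a complete-case model would drop patients without one.

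**Mortality.** From "with treatment arm as a covariate in the model" a reader might infer that the hazard ratio will have a needlessly wide interval. The calculation shows the opposite: the SE rises slightly and the estimate becomes a conditional hazard ratio, a different quantity.

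**Conclusion.** The point holds for intubation as a modest, inexpensive improvement. The planned comparison is valid but crude, while the baseline data are planned and the companion primary endpoint uses its own baseline. Whether and how to adjust is left open.

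The size is a variance reduction of roughly 0 to 18%, against a loss of about 2 to 3% if the covariates are uninformative. At the strong end of the range the 95% half-width falls from about 16.4 to 14.9 points. A 10-point imbalance in a 50% factor is common (about 30% of trials) but not the expected outcome.

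These figures depend on assumed event rates and prognostic odds ratios. The tabulated model held arm and two covariates without the SOFA stratum, so the gain from the full recommended model could differ somewhat. For mortality there is no precision argument; an adjusted Cox model can account for baseline imbalance and may gain a little power. Since all analyses are descriptive, no error-rate or power claim in the SAP is affected.

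**What to change.** Before database lock, amend section 7.11.1.2 to state:

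- **Main result:** the risk difference in Day 14 intubation with 95% CI, standardized over the analysed patients from a logistic model with arm, SOFA stratum (<6 versus ≥6), continuous baseline P(A-a)O2 and age. Name the interval method.
- **Missing baseline gradient:** keep the patient, for example by simple imputation of the covariate from baseline data only. Section 7.1.5 should say that its no-imputation rule covers outcomes, not this covariate.
- **Supportive:** one named crude test, Fisher or chi-square.
- **Short list:** no further covariates, and a stated fallback if the model fails to converge.

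Optionally, in section 7.11.2.2, report a Cox model with the same short covariate list beside the unadjusted one. Describe it as a conditional hazard ratio that accounts for baseline imbalance, not as a more precise version of the crude one.

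The cost is SAP wording and minor programming, with no new data. The downside is that events may be few, which limits the model to these covariates.
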